Key concomitant medications will be self-reported by the participant and over time will also be harvested from the PCORnet DataMart in CDM version 3.0 as it is deployed. Pre-randomization aspirin dose for aspirin users will be recorded. Participants will report key concomitant medications annually, either on the participant portal or during phone follow-up calls from the DCRI Call Center.

Details on the use of aspirin and important concomitant medications (P2Y₁₂ inhibitors) and other over-the-counter medications of interest (nonsteroidal antiinflammatory drugs [NSAIDS] and proton-pump inhibitors [PPIs]) will be collected from participants at baseline and annually during study follow-up. Details on other common secondary prevention medications prescribed (beta-blockers, angiotensin-converting enzyme inhibitors/angiotensin receptor blockers, and statins) will be collected from the CDM. The large trial population and randomization will minimize potential biases and confounding that could result from differential use of concomitant medications by randomized treatment assignment. A sensitivity analysis that accounts for concomitant medications as time-dependent covariates will be done to account for post-randomization treatments.

III.C.4. Schedule of Assessments

ADAPTABLE SCHEDULE OF ASSESSMENTS*

	Baseline	1-3 Week Follow-up Post-Randomization	Every 3 or 6 Month Follow-up	Annual Collection	End of Study
			*Assessments collected every three or six months based on randomization	Replaces 3M /6M follow up	
Video describing trial expectations	Х				
Check Key Eligibility Review	х				
Sign e-Consent	х				
Randomization and dose assignment	х				
Collect pre-randomization aspirin dose		x			
Collect demographic/contact information	X	Х			
Collect key concomitant (Rx and OTC) medications		х		х	х
Collect current aspirin dose/reason for DC		х	x	х	х
Collect hospitalizations		x	x	X	x
Collect Patient Reported Outcomes (PRO)	x		Q6 months		x
Insurance info/Confirmation at Contact info		x			

^{*}All Baseline and 1-3 Week Follow-up Post Randomization visit data will be collected at the Baseline visit for all non-internet patients with the exception of the current aspirin dose. The current aspirin dose will be collected 1-3 weeks following randomization.

III.C.5. Data Collection and Follow-up

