Assuming an annualized event rate of 4.6% in the higher risk arm and a 15% RR reduction (annualized event rate 3.8% in the lower risk arm) leads to 88% power and requires 1322 primary outcome events.

For the primary safety endpoint of hospitalization for major bleeding, power calculations were based on

Table 6					
Overall annualized event rate (%)	Relative Risk	Annualized event rate in low risk group (%)	Annualized event rate in high risk group (%)	Number of Events	Power
4.2	0.800	3.7	4.7	1321	0.99
4.2	0.825	3.8	4.6	1320	0.96
4.2	0.850	3.9	4.5	1322	0.88
4.4	0.800	3.9	4.9	1381	0.99
4.4	0.825	4.0	4.8	1381	0.97
4.4	0.850	4.1	4.8	1383	0.89
4.6	0.800	4.1	5.1	1441	0.99
4.6	0.825	4.2	5.0	1442	0.97
4.6	0.850	4.2	5.0	1439	0.90
4.8	0.800	4.3	5.3	1501	1.00
4.8	0.825	4.3	5.3	1502	0.98
4.8	0.850	4.4	5.2	1503	0.92

estimated primary event rates of 2%, 2.5%, and 3% per year (in the higher dose arm); annualized rate of loss to follow-up of 5%; 2-sided significance level alpha of 0.05; 7,500 participants in each treatment arm; total enrollment of 38 months; and a maximum follow-up period of 50 months. The power of the chosen testing strategy to detect a statistically significant difference in hospitalization for bleeding under these assumptions is shown in **Table 7**. Under all event rate scenarios, there will be power greater than 85% to detect an RR reduction of 25%, and for event rates of 2.5% or greater, power will be close to 80% to detect an RR reduction of 20%.

III.F.6. Secondary Endpoints

Secondary endpoints include the components of the primary endpoint, coronary revascularization procedures, quality of life, and functional status (Section III.A.5.a). Time-to-event outcomes will be analyzed using the same approach as the one used for the primary endpoint. Variables collected on numerical scales will be analyzed as continuous variables. Linear repeated measures mixed model will be employed to compare the 2 treatments on the changes from baseline.

Table 7			
Annualized event rate in higher-dose arm	Relative risk reduction	No. of events	Power
2%	25%	436	86%
	20%	449	66%
	15%	461	42%
2.5%	25%	544	92%
	20%	559	76%
	15%	575	50%
3%	25%	651	96%
	20%	669	83%
	15%	688	58%

III.F.7. Prior Treatment Effect

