Statistical Analysis Plan

Aspirin Dosing: A Patient-Centric Trial Assessing Benefits and Long-Term Effectiveness **"ADAPTABLE"**

Protocol History

Version 1.0	May 1, 2020
Version 1.1	December 7, 2020
Version 1.2	February 9, 2021

Prepared by

[name], MS Biostatistician III Duke Clinical Research Institute

[name] Director, Center for Predictive Medicine Duke Clinical Research Institute

[name] Professor of Biostatistics Duke Clinical Research Institute

1	Sy	nopsis	
2	Stu	udy Aims	
	2.1	.1 Aim 1	
	2.1	.2 Aim 2	
	2.1	.3 Aim 3	
3	Da	ta Sources	
4	Ra	ndomization and Drug Allocation	4
5	Stu	udy Endpoints	5
	5.1	Primary Endpoint	
	5.2	Secondary Endpoints	
	5.3	Primary Safety Endpoint	
6	lde	entification of Endpoints	5
7	Su	mmary of Statistical Methods	6
	7.1	Baseline Demographics and Medical History	6
	7.2	Populations for Analysis	7
	7.3	Primary Effectiveness Comparison	7
	7.4	Primary Safety Comparison	
	7.5	Censoring Rules	
	7.6	Power	
	7.7	Secondary Endpoints	9
	7.8	Prior Treatment Effect	
	7.9	Handling of Missing Data	
	7.9	.1 Outcome Dates	
	7.9	.2 Event-free Survival Outcomes	11
	7.9	.3 Longitudinal Outcome Data	11
	7.10	Planned Sensitivity Analyses	11
	7.11	Subgroup Analyses (Heterogeneity of Treatment Effect)	
8	Та	bles and Figures	
9	Re	ferences	

1 Synopsis

To identify the optimal dose of aspirin for secondary prevention in patients with atherosclerotic cardiovascular disease (ASCVD), we conducted a pragmatic clinical trial in which 15,000 patients who are at high risk for ischemic events were randomly assigned in a 1:1 ratio to receive an aspirin dose of 81 mg/day vs. 325 mg/day. Study participants were enrolled over 38 months. Maximum follow-up was 50 months (extended from originally specified 44 months). The primary endpoint is a composite of all-cause death, hospitalization for MI, or hospitalization for stroke. The primary safety endpoint is hospitalization for major bleeding with an associated blood product transfusion.

Additional details about the inclusion and exclusion criterion are contained in the study protocol. Many of the following details are also contained in the study protocol, with some differences in proposed statistical methodology.

2 Study Aims

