7.6 Power

Calculations were performed using PASS software. For the primary effectiveness endpoint, power calculations were based on an estimated primary event rate of 5.5% per year (in the higher risk arm), annualized rate of loss to follow-up of 5%, two-sided significance level α of 0.05, 7,500 patients in each treatment arm, enrollment of 38 months and a maximum follow-up period of 44 months. The power of the chosen testing strategy to detect a statistically significant

difference under these assumptions is 85% if the relative risk reduction is 15%, corresponding to a total of 1246 primary effectiveness events.

In November 2019, the DSMB approved extended follow-up in response to updated power calculations based on observed primary event rates. Assuming 7,500 patients in each treatment arm, annualized rate of loss to follow-up of 5%, two-sided significance level α of 0.05, enrollment of 38 months and maximum follow-up period extended to 50 months, the power to detect a relative risk reduction of 15% is 88% when the overall primary event rate is 4.5% in the higher risk arm, corresponding to a total of 1322 primary effectiveness events.

For the primary safety endpoint, power calculations were based on an estimated primary event rate of 2.5% per year (in the higher risk arm), annualized rate of loss to follow-up of 5%, two-sided significance level α of 0.05, 7,500 patients in each treatment arm, enrollment of 38 months and a maximum follow-up period of 44 months. The power of the chosen testing strategy to detect a statistically significant difference under these assumptions is 81% if the relative risk reduction is 20%, corresponding to a total of 642 primary safety events.

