7.7 Secondary Endpoints

Secondary endpoints include:

- All cause death
- Hospitalization for nonfatal MI
- Hospitalization for nonfatal stroke
- Coronary revascularization (PCI or CABG)
- Quality of life and functional status components include:
 - o Current Health
 - Physical function
 - Depression
 - Fatigue
 - Sleep disturbance
 - Social roles and activities
 - Pain Interference

Patient reported coronary revascularization events that do not match to one of the electronic sources will not be further verified. As such, these PROs will not be counted as events in the secondary event analyses.

All-cause death will be analyzed using a Cox proportional hazards model. All other time-to-event outcomes will be analyzed using the Fine and Gray method, equivalent to the Cox proportional-hazards model when competing risks are present, with all-cause death as the competing risk. The test will be two-tailed and will be performed at an overall α of 0.05. The proportional hazards assumption will be checked for randomized treatment arm using weighted Schoenfeld residuals. If there is evidence of non-proportionality, a cautious interpretation of the model hazard ratio will be encouraged, and non-parametric event rate estimates will be emphasized, as described for the primary effectiveness analysis.

Quality of life and functional status data are collected on numerical scales (1:excellent health-5:worst health). They will be analyzed as continuous variables. Mixed models using restricted maximum likelihood estimation (REML) will be employed to model trajectory of measures over time by treatment group. Mixed models account for the correlation structure imposed by repeated measures within participants while using all available data, from baseline to the end of the study, regardless of exact follow-up time. The intercept and slope will be modeled as random effects. The covariance structure for random effects will be modeled using an unstructured form. Time from baseline measurement and randomized treatment arm will be included in the model as fixed effect. Time will be tested for linearity using natural cubic splines. An interaction between randomized treatment arm and time will be assessed, as will the overall effect of randomized treatment arm.

Since these measures are discrete scores, it is expected that normality assumptions will not hold. Natural log and other appropriate transformations will be considered, as well as several distributions and link functions.

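### The mixed model for patient-reported scores treats baseline as a response and leaves the overall arm effect undefined; read as the arm coefficient, it understates the post-baseline difference

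*SAP*

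**What the plan says.** SAP 7.7 lists seven quality-of-life and functional-status components as secondary endpoints and analyses each with a mixed model fitted by REML.

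- **Response:** the model works by "using all available data, from baseline to the end of the study, regardless of exact follow-up time", so the baseline score is part of the outcome vector.
- **Fixed effects:** "Time from baseline measurement and randomized treatment arm will be included in the model as fixed effect". Baseline is not a covariate, and nothing sets the arm means equal at time 0.
- **Random effects:** "The intercept and slope will be modeled as random effects", with unstructured covariance. Linearity of time is to be checked with natural cubic splines.
- **Tests:** "An interaction between randomized treatment arm and time will be assessed, as will the overall effect of randomized treatment arm". The SAP does not say what the overall effect is (arm coefficient, time-averaged contrast or joint test), nor which of the two assessments answers the question.

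Protocol III.F.6 describes a different comparison for the same endpoints: "Linear repeated measures mixed model will be employed to compare the 2 treatments on the changes from baseline". SAP section 1 gives a general notice, "Many of the following details are also contained in the study protocol, with some differences in proposed statistical methodology", but does not explain this change.

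**The concern.** The baseline score precedes treatment, so its expected arm difference is zero by design. When it is one of the responses and arm enters as a single term, the arm coefficient is a weighted average of that known zero and the later differences. Adding the interaction does not rescue the arm coefficient, which then becomes the fitted difference at time 0.

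SAP 7.7 applies no multiplicity adjustment and leaves the results to the reader's interpretation. A coefficient reported as the overall effect of the randomized dose would therefore be taken as the treatment difference. If it is diluted, a larger sample makes the diluted value more precise but does not correct it. Leaving the term undefined also leaves the choice of contrast open until the data have been seen.

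**Working it through.** The documents give no power, SD, correlation or effect size for these scores, so there is no planned figure to reproduce. The calculation below is an illustration.

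**Inputs from the documents.** "7,500 patients in each treatment arm" (SAP 7.6). Patient-reported outcomes are collected at baseline, every 6 months and at end of study (Protocol III.C.4). Enrollment lasts 38 months and maximum follow-up is 50 months, so complete follow-up runs from 50 − 38 = 12 months to about 4 years, or 2 to 8 six-monthly assessments. Two-sided alpha of 0.05 is stated beside the time-to-event tests and carried over here.

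**Assumptions.** SD 1, within-patient correlation ρ of 0.4–0.7, random-slope SD of 0–0.1 per year unless stated otherwise, complete data.

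**Formulas** for m post-baseline visits, a constant shift d after baseline and no slope variance. In each case SE = √(2v/7,500), where v is the per-patient variance, and power ≈ Φ(z − 1.96).

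- Arm coefficient, no interaction: expectation d·m/(m+1); v = (1 + mρ)/(m+1).
- Post-baseline mean, baseline ignored: expectation d; v = (1 + (m−1)ρ)/m.
- Baseline constrained equal, or baseline as covariate, with a separate mean at each visit: expectation d; v = (1 + (m−1)ρ)/m − ρ².
- Linear arm-by-time slope: expectation d·Σ(t−t̄)/S, summed over post-baseline visits; v = (1−ρ)/S, with S = Σ(t−t̄)² over all visits.

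**Dilution of the arm coefficient.** m/(m+1) = 2/3 = 0.67, 4/5 = 0.80, 6/7 = 0.86 and 8/9 = 0.89 for m = 2, 4, 6 and 8. Without slope variance this does not depend on ρ. Slope variance lowers it somewhat, for example to 0.70 at 3 years with ρ = 0.7 and slope SD 0.2.

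**Worked example:** 2 years (m = 4), ρ = 0.6, d = 0.0309 SD, chosen so that the constrained model has 90% power.

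| Analysis | Expectation | v | SE | z | Power |
|---|---|---|---|---|---|
| Constrained or adjusted baseline | 0.0309 | 2.8/4 − 0.36 = 0.34 | 0.00952 | 3.25 | 90% |
| Post-baseline only, baseline ignored | 0.0309 | 2.8/4 = 0.70 | 0.01366 | 2.26 | 62% |
| Arm coefficient, no interaction | 0.8 × 0.0309 = 0.0247 | 3.4/5 = 0.68 | 0.01347 | 1.84 | 45% |
| Linear arm-by-time slope (S = 2.5) | 0.4 × 0.0309 = 0.0124 | 0.4/2.5 = 0.16 | 0.00653 | 1.89 | 47% |

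A joint 2-df test of arm and arm-by-time has noncentrality 1.84² + 1.89² ≈ 6.95 and power of about 65%.

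With the interaction kept, the arm coefficient in this example is the mean difference less slope times mean time: 0.8d − 0.4d × 1 = 0.4d. Under linear divergence from zero it is exactly 0. Neither value is the post-baseline difference.

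**Across the assumed range** (1–4 years, ρ 0.4–0.7, slope SD 0–0.1), with a constant shift sized for 90% power under the constrained model, the arm coefficient without interaction has about 30–66% power and the linear interaction about 21–71%. For ρ 0.4–0.6 the joint test has 51–77%.

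**Under linear divergence** (ρ 0.4–0.6, effect again sized for 90% power with a constrained baseline), the interaction is undiluted with 75–87% power. The arm coefficient recovers 0.36–0.50 of the end-of-follow-up difference, with 18–46% power.

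**The case against.** The strongest reply is that the dilution belongs to one reading of an undefined phrase. Placed directly after the interaction, the overall effect could be a joint test of arm and arm-by-time, which loses power but does not report an attenuated coefficient. That stands, so a reader who infers that the SAP's overall effect is certainly biased toward zero goes further than the text. What the text does support is an undefined contrast that is diluted under its simplest reading.

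A reader might also infer that the plan wastes the baseline score. That is in effect true of the arm coefficient: in the example, 45% power against 62% when baseline is ignored. It is not true of the planned analysis as a whole. The interaction in the same sentence uses baseline. Under linear divergence over 2–3 years its standard error is only about 3–21% larger than with a constrained baseline (ρ 0.4–0.7, slope SD 0–0.2). If the spline check leads to a non-linear arm-by-time term, that term could also pick up an early shift, and the power quoted for the linear slope would not apply.

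The constant shift also favours the recommended contrast, since it is exactly the pattern that the contrast estimates. The SAP expects non-normal scores and will consider transformations and other link functions, so the power figures are only indicative. The sample is also large: a 0.05 SD shift over 2–3 years would still be detected by the diluted test with 67–96% power (ρ 0.4–0.7, slope SD 0–0.2), against about 100% after the change. These points limit the consequence. They do not supply the missing definition or remove the attenuation from a reported arm coefficient.

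**Conclusion.** The point holds in a limited form. SAP 7.7 makes baseline a response with a free arm difference and does not define the overall arm effect. Neither version of the arm coefficient estimates the post-baseline difference: without the interaction it recovers about 0.67–0.89 of a constant shift over 2 to 8 assessments, and with it the coefficient refers to time 0. The interaction is sound for linear divergence but weak, as a linear slope, for an early shift that persists.

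The m/(m+1) factors rest on a constant shift, complete data and no slope variance. The power figures rest further on assumed correlations, slope SDs and follow-up lengths that the documents do not give. Type I error is not inflated. The primary effectiveness and safety analyses are untouched, so this is a correction to the secondary patient-reported analyses only.

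**What to change.** In SAP 7.7, either constrain the arm means to be equal at baseline, with arm terms at post-baseline times only, or include the baseline score as a covariate and model post-baseline scores only. Name the average post-baseline arm difference as the treatment contrast, and keep the arm-by-time interaction as a supporting test. State how this relates to the change-from-baseline comparison in Protocol III.F.6, so that the two documents describe the same question.

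The cost is a changed model statement, with no new data. The covariate form drops patients without a baseline score or without any post-baseline score. The constrained form keeps them and is the easier choice if either kind of gap is common.

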7.8 Prior Treatment Effect

We expect that most patients recruited into the ADAPTABLE trial will already be treated with pre-randomization aspirin therapy, given the nature of the inclusion criteria and the known high utilization of aspirin for the secondary prevention of coronary artery disease in the United States. Therefore, a sensitivity analysis for the primary efficacy and safety endpoints with a 10-day landmark will be performed that excludes events occurring in the first 10 days following randomization to account for the expected time period of washout from the pre-randomization aspirin dose.

7.9 Handling of Missing Data

Concerted effort will be made to eliminate or minimize the occurrence of missing data. Participants will grant access to their electronic medical records at enrollment and during study follow-up as well as to have their information searched in national databases. During the course of the trial, missing data has been monitored by the operations team via aggregate reports. The DCRI call center has been responsible for locating participants with 2 consecutive missed study visits who have not been confirmed dead through electronic data queries or through contacts with the site research teams. This process has changed since study initiation so that participants are now contacted if there is no completed visit in the prior 6 months.

If, despite these efforts, missing data occur, we will employ statistical techniques appropriate to the type of data, as described below.

Reasons for missing data will be collected and described, including withdrawal of consent for any follow-up and loss to follow-up for portal visits. Descriptive statistics for key baseline characteristics and clinical events prior to study withdrawal or completion will be presented by subgroups defined by availability of follow-up data and by treatment group. All participants in the defined study population will be accounted for in all analyses and presentations.

7.9.1 Outcome Dates

Any partial or completely missing date for a confirmed primary effectiveness or safety outcome at the time of database lock will be imputed as follows:

- If the day is missing, 15th of the month, or the randomization date (if patient randomized after 15th of the same month and same year) will be used;
- If the month is missing, June, or the randomization month (if patient randomized after June and year of the event is same as randomization year) will be used;
- If the complete date is missing, the midpoint between the date of last known event-free visit and end of follow-up will be used.

7.9.2 Event-free Survival Outcomes

For the primary and secondary analyses based on event-free survival, most participants are expected to have at least one source of data for these endpoints (patient portal with confirmation of reported events, CDM, CMS or private claims). Issues with potential incomplete data will be addressed through sensitivity analyses described in Section 7.10. Participants discontinuing the study prematurely and withdrawing consent for trial follow-up will be considered truly missing and will be censored at the time of discontinuation. This approach might lead to biased results if the mechanism of discontinuation is non-ignorable, i.e. the hazard for a censored participant is not the same as that of uncensored participants, conditional on observed data. If more than 5% of participants withdraw consent for trial follow-up, then a tipping point analysis similar to that described by Little et al (2016) will be conducted to assess impact of potential non-ignorable censoring on inference for the primary analysis. A Weibull model of the primary endpoint will be fit to the entire ITT population, with independent variables including an indicator of withdrawal of consent for electronic follow-up and selected baseline characteristics. Other independent variables may be considered. The Weibull model will yield an estimated hazard at the time of withdrawal of consent for each participant adjusted for selected covariates. We then assume that the hazard for a participant who withdraws consent is different from those who do not and allow that difference to vary between treatment groups. An inflation factor will be applied to the hazards, with different inflation factors applied to each treatment group. The resulting hazards will be used to impute events to the end of trial follow-up assuming a Weibull distribution. A Cox model as specified for the primary analysis will be fit to the resulting dataset and treatment effect hazard ratio will be estimated, with standard errors adjusted using standard multiple imputation combining rules. The resulting inference will be examined across a range of clinically plausible inflation factors; if inference from primary analysis is maintained then the results will be considered robust. To aid in interpretation, the mean number of imputed events will be reported for inflation factors.

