7.5 Censoring Rules

In the event that a patient does not experience an efficacy or safety endpoint, the patient will be censored at the earliest of study end date or maximum follow-up time point at which the patient can be reasonably assumed to be event free. The maximum follow-up time point will be determined from any of the following data sources: CDM censor date, CMS censor date, private health insurance censor date, or the web portal censor date (last point of contact).We expect the study end date to occur on or before all follow-up time points; however, for completeness, censoring dates are defined below. Patients who withdraw consent for trial follow-up will be censored at the time consent is withdrawn. Patients who consent to limited participation follow-up will be censored at the earliest follow-up time point as delineated.

The censoring date for CDM data will be at the site-specific censoring date, which is determined by the PCORnet Distributed Research Network Operations Center based on data curation query results. The censoring date for CMS will be the minimum of the end of enrollment in fee-forservice or the last date claims data are available. The censoring date for private health insurance claims will be the minimum of the end of claims enrollment or the last date claims data are available.

Time to event modeling will include the first occurrence of an event where the time to event is calculated as the event date – randomization date +1.

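### The withdrawal indicator in the SAP 7.9.2 Weibull model can make the tipping-point base hazard too low, because the SAP does not say how the indicator is coded or set at prediction

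*SAP*

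**What the plan says.** SAP 7.5 gives the rule for the primary analysis: "Patients who withdraw consent for trial follow-up will be censored at the time consent is withdrawn". SAP 7.9.2 accepts that this may bias the result if censoring is non-ignorable, which it describes as a censored participant's hazard differing from that of uncensored participants given the observed data. The response is conditional: "If more than 5% of participants withdraw consent for trial follow-up, then a tipping point analysis" is to follow.

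The steps of that analysis are:

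- A Weibull model for the primary endpoint is fitted to all ITT participants, withdrawers included. Its covariates are given in these terms: "with independent variables including an indicator of withdrawal of consent for electronic follow-up and selected baseline characteristics".
- "The Weibull model will yield an estimated hazard at the time of withdrawal of consent for each participant adjusted for selected covariates".
- The SAP then supposes that withdrawers' hazard differs from that of other participants, by an amount that may vary by arm: "An inflation factor will be applied to the hazards, with different inflation factors applied to each treatment group".
- Events are imputed to the end of follow-up, the primary Cox model is refitted, and the results are pooled by multiple-imputation rules.
- Over a clinically plausible range of factors, "if inference from primary analysis is maintained then the results will be considered robust". In addition, "the mean number of imputed events will be reported for inflation factors".

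The SAP leaves four things open: whether the indicator is fixed or changes with time, whether it covers withdrawal after a first event, whether it is 1 or 0 when the hazard is predicted, and which numerical factors will be tried.

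**The concern.** Withdrawal is not known at randomization. A time-fixed flag for it sorts people by something in their future: to be flagged, a person had to stay alive, and under one coding free of any first event, until the day of withdrawal. The model reads that forced survival as low risk, and the inflation factor then multiplies the result.

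The SAP's own description of non-ignorable censoring compares withdrawers with people who remain. The pattern-mixture analysis in Protocol III.F.8 likewise measures its offset from participants who do not drop out. Factor 1 should therefore mean the same hazard as those who stay. If the base is too low, a stated factor of 2 or 3 stresses the result less than it appears to, and the robustness rule is met too easily.

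This matters because it is the only analysis in SAP 7.9.2 that lets withdrawers' hazard differ from that of the others. The inverse probability weighting for premature discontinuation in Protocol III.F.8 is not carried into that section.

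**Working it through.** SAP 7.9.2 states no computed figure, so there is none to reproduce. The check asks what base hazard the described model yields when withdrawal is unrelated to outcome, so that the true withdrawer-to-other ratio is 1.0.

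**Inputs from SAP 7.6:** 7,500 per arm; 4.5% per year in the higher-risk arm; 15% relative risk reduction, simulated as a hazard ratio of 0.85; 38 months' accrual (taken as uniform); 50 months' maximum follow-up; two-sided 0.05.

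**Assumptions not in the documents:** withdrawal at about 2%, 2.5% or 5% per year (5% borrows the SAP's loss-to-follow-up rate as an upper stand-in); 30%, 50% or 70% of first events fatal; 8% per year mortality after a nonfatal first event.

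**Step 1: the codings.**

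- *A, flag marks people censored by withdrawal.* No flagged person has a first event. With coefficient b and cumulative baseline hazard H, the flagged group's log-likelihood is 0·b − exp(b)·ΣH, which rises without limit as b falls. The estimate diverges and the hazard goes to zero.
- *B, flag marks anyone who ever withdrew.* Nonfatal first events before withdrawal count, but death cannot precede withdrawal. The flagged group therefore lacks fatal first events by construction.
- *C, no flag.* Withdrawers are simply censored.
- *Time-dependent flag.* It switches on when a full withdrawer's analysed follow-up ends, so there is no time at risk from which to estimate its coefficient.

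**Step 2: fitted ratio for the flag** (true value 1.0; 20 simulated trials per setting; ranges are over withdrawal rates).

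| Fatal share of first events | A | B |
|---|---|---|
| 30% | about 0 | 0.66–0.69 |
| 50% | about 0 | 0.45–0.46 |
| 70% | about 0 | 0.25–0.28 |

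**Step 3: imputed hazard divided by the true hazard** (50% fatal share).

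| Withdrawn | A, flag at 1 | B, flag at 1 | A, flag at 0 | B, flag at 0 | C |
|---|---|---|---|---|---|
| 5.9% | 0 | 0.495 | 1.038 | 1.021 | 1.002 |
| 11.5% | 0 | 0.478 | 1.072 | 1.036 | 0.996 |

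These agree with Step 2: at 5% withdrawal per year B's fitted ratio was 0.456, and 0.456 × 1.036 = 0.472, close to 0.478.

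**Step 4: effect on the tipping point.** One simulated dataset per withdrawal rate, 50% fatal share, flag at 1 for A and B. Factors from 1 to 10 were applied in the lower-hazard arm only, with 20 imputations and pooled Cox results. Before imputation the hazard ratio was 0.847 (z −3.16) with 11.4% withdrawn and 0.851 (z −3.14) with 4.9% withdrawn.

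| Withdrawn | Model | Events imputed at factor 1 | z at factor 2 | z at 3 | z at 5 | Significance lost at |
|---|---|---|---|---|---|---|
| 11.4% | A | 0 | −3.20 | −3.20 | −3.20 | none up to 10 |
| 11.4% | B | 38.5 | −2.72 | −2.19 | −1.34 | 3–4 |
| 11.4% | C | 106.5 | −1.91 | −0.85 | 0.92 | 1.5–2 |
| 4.9% | A | 0 | −3.18 | −3.18 | −3.18 | none up to 10 |
| 4.9% | B | 24.1 | −2.89 | −2.50 | −1.99 | 5–6 |
| 4.9% | C | 46.0 | −2.55 | −1.99 | −1.27 | 3–4 |

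The 4.9% rows lie just under the 5% trigger and are shown for scale only. B's imputed counts relative to C's are 38.5/106.5 = 0.36 and 24.1/46.0 = 0.52. They scatter around the averages in Step 3 because each is a single dataset.

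**The case against.** The strongest reply is that the SAP does not prescribe the harmful step. The bias needs the hazard to be predicted with the indicator at 1, and the text does not say so. Its order of steps, first a hazard and then an assumed difference for withdrawers entering through the inflation factor, is compatible with a reference hazard for people who stay. So is the offset in Protocol III.F.8. On that reading the base hazard is only 2% to 7% too high. This stands, and it makes the point conditional. It does not rescue the covariate, since leaving it out gives 0.996 to 1.002 times the true hazard.

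A reader might infer that the SAP treats withdrawal as a baseline covariate, that withdrawers therefore have almost no first events, and that the base hazard is near zero or halved. The documents do not support that. The indicator is listed beside the baseline characteristics, not among them. The absence of events holds only for coding A, and a halving needs a fatal share near 50%, which the documents do not give.

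The wording of the indicator also differs from that of the trigger: one concerns consent to electronic follow-up, the other consent to trial follow-up. SAP 7.5 recognises limited participation, and the table in SAP 7.10 has participants with self-report but neither CDM nor claims data. If the indicator includes people who stop only electronic access, they can still have counted events and coding A's zero fails. That is fair, and it is a second matter to reconcile.

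Finally, the reported mean number of imputed events would expose a zero. It would be a weaker guard against a partial shortfall, and the robustness rule turns on the inference, not on that count.

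**Conclusion.** The concern holds in a conditional form, with medium confidence. With a time-fixed indicator at each withdrawer's own value, the base hazard is zero (coding A) or too low (coding B: fitted ratio about 0.25 to 0.69 for fatal shares of 70% to 30%). Factor 1 is then not the ignorable case, and the error favours a finding of robustness. With 11.4% withdrawn in the simulated example, the same data tip at 1.5–2, at 3–4, or not at all up to 10, depending on a choice the SAP leaves unstated.

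It would go too far to say that no inflation factor could change the inference. That is true only under coding A; under coding B the analysis does tip, but later. Nor is it shown that the trial's own robustness conclusion would change, since the SAP gives no factor range and the analysis runs only above 5% withdrawal. The sizes rest on the assumed withdrawal rates, fatal shares and later mortality, on withdrawal unrelated to outcome, and, for the tipping points, on single datasets. The SAP models its method on a cited 2016 paper that could not be consulted here.

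**What to change.** Remove the withdrawal indicator and fit the Weibull model on arm and the selected baseline covariates, with withdrawers censored at withdrawal. If the indicator is kept, state that the reference hazard is predicted with it at 0.

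Apply the arm-specific factors to the conditional hazard after the withdrawal time, and state that factor 1 in both arms is the ignorable case. Use one definition of withdrawal for the trigger, the censoring and the imputation, and say how people who stop only electronic follow-up are handled. Pre-specifying the numerical range of factors would make the robustness rule checkable.

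The cost is one deleted covariate and a few sentences. No new data are needed, and the primary analysis is unchanged.
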